7.6.2.4 Other Secondary Categorical Endpoint

The other secondary categorical endpoint is responders with the following criteria:

- Patients with normalization of liver enzymes in the subset of patients with increased baseline value

Normalization of liver enzymes (ALT, AST, GGT or ALP) will be analyzed in the subset of patients with baseline greater than the upper reference range for the respective liver enzyme parameter. Patients will be classed as responders if the liver enzyme normalizes, i.e. decreases to < upper reference range at a post baseline visit.

Responder rate will be provided within each treatment group. Patients who have no assessments at a particular visit will be defined as non-responders. The stratified CMH will primarily be used to analyze the responders, stratifying for T2DM status (T2DM patients versus non-T2DM patients) and NASH CRN fibrosis scoring system (F1 versus F2/F3). Each PXL065 treatment group will be compared with placebo. The OR, 95% CIs for the OR, and p-values will be displayed for the ITTS. In addition, the number of responders and non-responders will be displayed for each treatment group, see Appendix C for example SAS code.

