#### *9.5.3.4 Clinical Laboratory Data*

Laboratory findings will be evaluated using central laboratory's normal reference ranges. Clinically relevant values will be flagged (please refer to central laboratory manual). Descriptive statistics will be derived for quantitative laboratory parameters for each treatment group and timepoint. Similarly, changes from the baseline will be summarized.

Values outside the normal range (N) will be categorized as H (above the normal range) or L (below the normal range) based on the central laboratory's normal reference range. Shift tables will be presented at each post-baseline visit showing the number of patients per treatment group with N, H or L.

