2.4 COVID-19

The COVID-19 memo provided alternative processes relative to those described in the protocol that may be used to conduct the study if needed to ensure subject safety and/or minimize impact on study integrity during the COVID-19 pandemic. For example, the screening window according to the memo can be extended from 8 weeks to 12 weeks. The visit window for Visit 2 and 3 can also be extended from ± 4 days to 6 days. In addition, laboratory assessments can also be done locally if they cannot be collected for central laboratory testing and visits can be done virtually by phone or telehealth calls. However, if there are two consecutive virtual visits then the next one needs to be on-site.

Additional data related to COVID-19 will now also be collected for example, patients discontinuing due to COVID, patients failing screening due to COVID, patients missing visits due to COVID, interruption of study treatment due to COVID and missed visits due to COVID. This data will be presented in tables and listings.

Statistical Analysis Plan

Sponsor Name: Poxel
Sponsor Protocol ID: PXL065-003

3. Efficacy and Safety Variables

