3.2 Secondary Efficacy Endpoints

- Absolute change in the percentage of LFC (assessed by MRI-PDFF) from baseline to Week 36 (V8-EoT)
- Response defined as an absolute reduction in LFC $\geq 5\%$ from baseline to Week 36 (V8-EoT)
- Response defined as a relative reduction in LFC $\geq 30\%$ from baseline to Week 36 (V8-EoT)
- Response defined as a relative reduction in LFC $\geq 50\%$ from baseline to Week 36 (V8-EoT)
- Response defined as a LFC value at Week 36 (V8-EoT) that is normalized, i.e. $\leq 5\%$
- Change in the following parameters from baseline to Week 36 (V8-EoT):
 - Liver enzymes: Alanine aminotransferase (ALT), Aspartate aminotransferase (AST), gamma-glutamyl transferase (GGT), alkaline phosphatase (ALP)
 - Percentage of responders as defined by the percentage of patient with normalization of liver enzymes in the subset of patients with increased baseline value
 - Measured glycemic parameters: Fasting plasma glucose (FPG), Glycated hemoglobin (HbA1c), serum insulin, C-peptide
 - Insulin resistance indexes: Homeostasis model assessment of insulin resistance (HOMA-IR), Quantitative insulin sensitivity check index (QUICKI), Homeostasis model assessment of β -cell function (HOMA- β) and Adipose tissue insulin resistance (Adipo-IR)

Exploratory endpoints

Change from baseline in the following parameters at Week 36 (V8-EoT):

- Adiponectin
- Lipids: total cholesterol, low-density lipoprotein cholesterol (LDL-c), high-density lipoprotein cholesterol (HDL-c), triglycerides, free fatty acids (FFA)
- Biomarker of inflammation: High-sensitivity C-reactive protein (hsCRP)
- Biomarkers of fibrosis: N-terminal type III collagen propeptide (pro-C3), NAFLD Fibrosis score (NFS) and Fibrosis 4 (FIB-4) score and Enhanced Liver Fibrosis (ELF) score
- Histological change in liver biopsy:
 - Change in NAFLD Activity Score (NAS), in each component of NAS (steatosis, ballooning and inflammation) and in NASH CRN fibrosis score
 - Improvement in each component of NAS (steatosis, lobular inflammation and hepatocellular ballooning) by ≥ 1 point without worsening of fibrosis
 - Improvement in NAS by ≥ 2 points without worsening of fibrosis
 - Improvement in NASH CRN fibrosis score by ≥ 1 point

Statistical Analysis Plan

Sponsor Name: Poxel
Sponsor Protocol ID: PXL065-003

- NASH resolution (NAS score of 0-1 for inflammation, 0 for ballooning, and any value for steatosis)

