7.7.3.1 Standard Safety Laboratory Panel

Data for the following hematology, biochemistry, urinalysis and coagulation received from central laboratory will be listed for the Safety set with site 065-S and summarized by treatment group and visit for the Safety set. Local laboratory results will be listed only.

Hematology	Biochemistry	Urinalysis
Erythrocytes Hemoglobin Hematocrit Red Blood Cell Morphology Mean corpuscular volume Mean corpuscular hemoglobin Mean corpuscular hemoglobin concentration Leucocytes Differential blood count (lymphocytes, monocytes, eosinophils, basophils, neutrophils/ absolute values and percentages should be given) Thrombocytes	Blood Urea Nitrogen Creatinine Sodium Potassium Chloride Bicarbonate Calcium Inorganic phosphate Total protein Albumin Uric acid Creatine phosphokinase AST ALT GGT Total bilirubin ALP hsCRP TSH (during Screening Period only)	pH Specific gravity Protein Glucose Ketones Nitrites Urobilinogen Blood Leucocytes If the dipstick result is abnormal: microscopic examination of the sediment for blood cells, cylinders, etc.

Coagulation
Activated Partial Thromboplastin Time (aPTT) Prothrombin Time International Normalized Ratio (INR)

Values outside the normal range will be categorized as H (above the normal range) or L (below the normal range) based on the central laboratory's normal reference range. Laboratory data will be summarized by visit using standard descriptive statistics. Changes from baseline will also be summarized.

The following elevations will be assessed:

Predefined Limits of Change (PDLC)
ALT (SGPT) (U/L) Value >3xULN
ALT (SGPT) (U/L) Value >5xULN
ALT (SGPT) (U/L) Value >8xULN
AST (SGOT) (U/L) Value >3xULN
AST (SGOT) (U/L) Value >5xULN
AST (SGOT) (U/L) Value >8xULN
Total Bilirubin (μmol/L) Value >2xULN

Statistical Analysis Plan

Sponsor Name: Poxel
Sponsor Protocol ID: PXL065-003

Predefined Limits of Change (PDLC)

ALP (U/L)	Value >2xULN
-----------	--------------

A listing of patients with elevated PDLC criteria will be produced for Safety set with site 065-S .

7.7.3.2 eGFR

Data for eGFR received from central laboratory will be listed and summarized by treatment group and visit. Local laboratory results will be listed only.

eGFR will be calculated using the chronic kidney disease – epidemiology collaboration (CKD-EPI) formula, as follows [14]:

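### SAP 7.6.2.4 does not tie liver-enzyme normalization to Week 36, as SAP 3.2 does, and scores a value equal to the upper reference limit as a non-response

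*SAP*

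**What the plan says.** SAP 3.2 lists the secondary endpoints. Under the lead-in "Change in the following parameters from baseline to Week 36 (V8-EoT") it includes: "Percentage of responders as defined by the percentage of patient with normalization of liver enzymes in the subset of patients with increased baseline value". The protocol synopsis has the same structure. Protocol 9.5.2.3 repeats the endpoint without a visit and leaves the analysis to the SAP.

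SAP 7.6.2.4 supplies that analysis. The population is restricted to patients "in the subset of patients with baseline greater than the upper reference range for the respective liver enzyme parameter". The response rule is: "Patients will be classed as responders if the liver enzyme normalizes, i.e. decreases to < upper reference range at a post baseline visit". The missing-data rule is: "Patients who have no assessments at a particular visit will be defined as non-responders". Each dose is compared with placebo by a stratified Cochran-Mantel-Haenszel analysis.

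On what counts as abnormal, Protocol 9.5.3.4 says: "Values outside the normal range (N) will be categorized as H (above the normal range"), with L for values below it. SAP 7.7.3.1 uses the same H and L categories.

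The four enzymes belong to the standard safety panel. After baseline that panel is drawn at Weeks 12, 24, 36 and 38 (Protocol Table 1; SAP 6.1, Table 1, Group 3). The last dose is taken at the Week 36 visit (Protocol 6.2.1), so Week 38 is off treatment.

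**The concern.** A responder definition has to settle which measurement decides the outcome and which values pass. SAP 7.6.2.4 leaves the first open and sets the second against the plan's own convention.

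On the visit, neighbouring sections are explicit. All four liver-fat responder definitions in SAP 7.6.2.2 name Week 36, and so does the enzyme change-from-baseline analysis in SAP 7.6.2.3. Section 7.6.2.4 does not. Two programmers could follow its text faithfully and report different percentages for the same secondary endpoint, one of them counting patients who are above the limit at end of treatment.

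On the cut-off, a patient can be normal in the laboratory categories and a non-responder here, on the same value at the same visit.

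**Working it through.** The plan states no rate, sample size or power for this endpoint, so there is no figure to reproduce. The check compares the texts and then sizes each discrepancy under stated assumptions.

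**Visit: three readings**

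| Reading | Support in the text | Patient below the limit at Week 12 only | Patient below the limit at Week 38 only |
|---|---|---|---|
| Week 36 only | SAP 3.2, synopsis | non-responder | non-responder |
| Any post-baseline visit | literal wording of the response rule | responder | responder |
| Each visit separately | the missing-data sentence | responder at Week 12, not at Week 36 | responder at Week 38, not at Week 36 |

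The missing-data sentence fits the third reading better than the second: if any visit sufficed, one missed visit would not decide a patient's status. The third reading still does not say which visit is the endpoint. It yields up to 4 enzymes x 3 doses x 4 visits = 48 dose-placebo comparisons, including an off-treatment visit, against 4 x 3 = 12 at Week 36 alone.

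**Visit: how far the readings could diverge**

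Let p be the chance of a value below the limit at one visit. If the four visits were independent, the any-visit rate would be 1 - (1 - p)^4:

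- p = 0.20: 1 - 0.80^4 = 1 - 0.4096 = 0.59
- p = 0.30: 1 - 0.70^4 = 1 - 0.2401 = 0.76

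Repeated enzyme values are correlated, which narrows the gap. In a latent-normal simulation with an equal between-visit correlation, the any-of-four rates were:

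| Single-visit rate | correlation 0.5 | correlation 0.8 |
|---|---|---|
| 0.20 | 0.44 | 0.34 |
| 0.30 | 0.59 | 0.47 |

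The rates and correlations are assumptions; neither document gives them.

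**Boundary: consistency**

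| Value | Baseline subset (SAP 7.6.2.4) | Response (SAP 7.6.2.4) | Laboratory category |
|---|---|---|---|
| above limit | included | no | H |
| equal to limit | not included | **no** | **not H** |
| below limit (within range) | not included | yes | not H |

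A value equal to the limit is neither raised at baseline nor normalized later. The laboratory categories treat it as normal.

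**Boundary: size**

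Assume integer reporting, an upper limit of 40 U/L, and log-normal values with median m and log-scale SD s. The share of values reported as exactly 40 is

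Phi[(ln 40.5 - ln m)/s] - Phi[(ln 39.5 - ln m)/s].

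- m = 40, s = 0.3: Phi(0.041) - Phi(-0.042) = 0.033
- m = 60, s = 0.3: 0.013

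For m from 35 to 60 and s from 0.3 to 0.5 the share runs from 1.3% to 3.3%.

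**The case against.** The strongest reply is that the timing is already settled elsewhere. SAP 3.2 and the synopsis give Week 36, and the missing-data sentence implies visit-by-visit classification, so a fall at Week 12 would count for Week 12 only. The example code to which the section refers is redacted and may fix both visit and cut-off. This reply stands against any claim that the plan counts transient normalization; that is one literal reading only. It does not remove the need to bring the two sections into agreement, because the sentence that defines response still names no visit.

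A reader might also infer that the rule doubles the placebo response rate. With an assumed between-patient SD of log ALT of 0.45, a median of 1.0 to 1.2 times the limit and a within-patient SD of 0.15 to 0.35, simulated placebo rates are 10-29% at Week 36 and 19-52% at any of Weeks 12, 24 or 36. Those inputs are not in the documents, and the second range applies only under the any-visit reading. Nor does the comparison weaken in that model. With an assumed 25% reduction in enzyme level on active drug, the active-minus-placebo difference is 20-33 points at Week 36 and 24-37 points under any of the three visits. The issue is what the percentage means, not a demonstrated bias.

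A third inference is that patients with only a local laboratory result become failures. SAP 2.4 says that "laboratory assessments can also be done locally if they cannot be collected for central laboratory testing", and SAP 7.7.3.1 says "Local laboratory results will be listed only". The second sentence sits in the safety section, however, and no efficacy section says that a local value is no assessment. Scoring local values against local ranges would also depart from the central-laboratory measurement and ranges in Protocol 8.3.6 and 9.5.3.4. This inference is not part of the point.

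Finally, this is one secondary endpoint without multiplicity control, and the same enzymes are analysed as continuous outcomes at Week 36. That is correct, and it limits the weight of the point.

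**Conclusion.** The point holds in two parts. SAP 7.6.2.4 does not match the Week 36 time point that SAP 3.2 and the synopsis set for the same endpoint, and its wording allows an any-visit or a by-visit count. Its strict cut-off contradicts the convention that only values above the range are high.

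The boundary contradiction is definite but small: a few percent of values under the assumed limit, medians and SDs, under a rule that applies alike to all arms. The visit discrepancy could matter more for the reported percentage, but its size depends on which reading is programmed and on enzyme variability that the documents do not give. Neither part touches the primary analysis. The correction changes who is classed as a responder and is worth making because it costs so little.

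**What to change.** In SAP 7.6.2.4, define a responder as a patient whose baseline value is above the upper reference limit and whose Week 36 (V8-EoT) value is at or below it. Report Weeks 12 and 24 only as separate by-visit rates, and leave Week 38 out of the efficacy endpoint. Confirm that the example code follows the same visit and inequality.

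The cost is a few words and one derivation. The downside is that the responder percentage may be lower than an any-visit count would give. Moving to an at-or-below cut-off works slightly the other way.

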7.6.2.5 Subgroup Analysis

Analysis of responder defined as relative reduction in LFC $\geq 30\%$ from baseline to Week 36 (V8-EoT), will have a subgroup analysis performed using multiple imputation as per Section 7.6.1.1 for the following groups:

- Randomization strata of T2DM status (T2DM patients, non-T2DM patients)
- Randomization strata of NASH CRN fibrosis scoring system (F1, F2/F3)

The MMRM analysis described in Section 7.6.2.3 will have subgroup analysis performed for the following parameters and subgroups in the ITT Set:

- ALT (U/L)
 - Randomization strata of T2DM status (T2DM patients, non-T2DM patients)
 - Randomization strata of NASH CRN fibrosis scoring system (F1, F2/F3)
- AST (U/L)
 - Randomization strata of T2DM status (T2DM patients, non-T2DM patients)
 - Randomization strata of NASH CRN fibrosis scoring system (F1, F2/F3)
- FPG (mmol/L)
 - Randomization strata of T2DM status (T2DM patients, non-T2DM patients)
- HbA1c (%)
 - Randomization strata of T2DM status (T2DM patients, non-T2DM patients)

Statistical Analysis Plan

Sponsor Name: Poxel
Sponsor Protocol ID: PXL065-003

7.6.3 Exploratory Endpoints

The analyses described in Section 7.6.2.3 will be repeated for the ITTS for the following endpoints:

- Adiponectin
- Lipids (Percentage change): total cholesterol, LDL-c, HDL-c, triglycerides, FFA
- Biomarker of inflammation: hsCRP

For lipids (total cholesterol, LDL-C, HDL-C, triglycerides and FFA) summary statistics will be provided for both, absolute and percent change from baseline.

Biomarkers of fibrosis (pro-C3, NFS, FIB-4 and ELF score) will be analyzed using a linear regression with the following covariates, treatment, T2DM status (T2DM patients versus non-T2DM patients) and NASH CRN fibrosis scoring system (F1 versus F2/F3), and for the baseline endpoint specific parameter value. LSMs for treatment groups, standard error of the LSM, pairwise differences (PXL065 7.5 mg QD, 15 mg QD and 22.5 mg QD versus placebo) in LSMs, p-values and 95% CIs will be presented. In addition, descriptive statistics for each parameter and change from baseline will be calculated by visit within each treatment group.

The change from baseline in NAS, in each component of NAS (steatosis, ballooning and inflammation), total NAS score and in NASH CRN fibrosis score will be analyzed using a non-parametric ANCOVA method of Koch, Tangen, Jung, and Amara (Koch et al), with fixed effects for treatment, stratification factors, i.e. T2DM status (T2DM patients versus non-T2DM patients) and NASH CRN fibrosis scoring system (F1 versus F2/F3), baseline endpoint specific parameter value. This analysis will be performed using the SAS macro for non-parametric randomization-based ANCOVA 'NParCov4'. An example of the SAS code is given below:

Corporate confidential information

Note: The variance under the null (HYPOTH=NULL) will be the structure for producing p-values, while the variance under the alternative (HYPOTH=ALT) will be used for computing confidence intervals.

Total NAS score is the sum of three scores:

- Steatosis (0-3)

CONFIDENTIAL

Statistical Analysis Plan

Sponsor Name: Poxel
Sponsor Protocol ID: PXL065-003

- Ballooning (0-2)
- Inflammation (0-3)

The statistical model will be used to calculate the treatment difference (PXL065 - placebo), 95% CI and p-value at Week 36

The number of percentage of patients in each category below from baseline to Week 36 will also be presented by treatment group on the ITTS:

- Improvement in each component of NAS (steatosis, lobular inflammation and hepatocellular ballooning) by ≥ 1 point without worsening of fibrosis
- Improvement in NAS ≥ 2 points without worsening of fibrosis
- Improvement in NASH CRN fibrosis score by ≥ 1 point
- NASH resolution (NAS score of 0-1 for inflammation, 0 for ballooning, and any value for steatosis)
- NASH resolution (NAS score of 0-1 for inflammation, 0 for ballooning, and any value for steatosis) with improvement in NASH CRN fibrosis score by ≥ 1 point
- NASH resolution (NAS score of 0-1 for inflammation, 0 for ballooning, and any value for steatosis) with no worsening in NASH CRN fibrosis score
- NASH resolution (NAS score of 0-1 for inflammation, 0 for ballooning, and any value for steatosis) and improvement in NAS ≥ 2 points with no worsening in NASH CRN fibrosis score

For each response, responder rate will be provided within each treatment group for patients with Week 36 assessments. The stratified Cochran-Mantel-Haenszel (CMH) will primarily be used to analyze the responders, stratifying for T2DM status (T2DM patients versus non-T2DM patients) and NASH CRN fibrosis scoring system (F1 versus F2/F3). Each PXL065 treatment group will be compared with placebo. The odds ratios (ORs), 95% CIs for the ORs, and p-values will be displayed for the ITTS. In addition, the number of responder's and non-responders will be displayed for each treatment group, see for example SAS code.

A listing of these endpoints will also be produced for the ITTS-w-065-S .

In addition, the following categories will be summarized for responders/non-responders by treatment group in the ITTS in the subpopulation of responders for LFC (defined as patients with a Relative Reduction in LFC (%) $\geq 30\%$ at Week 36):

- NASH resolution (NAS score of 0-1 for inflammation, 0 for ballooning, and any value for steatosis) with No Worsening in NASH CRN Fibrosis Score from Baseline to Week 36
- Improvement in NASH CRN Fibrosis Score of At Least One Point from Baseline to Week 36

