: Fibrosis biomarkers include: N-terminal type III collagen propeptide (pro-C3), Nonalcoholic Fatty Liver Disease (NALFD) Fibrosis Score (NFS), Fibrosis 4 (FIB-4) score and Enhanced Liver Fibrosis (ELF) score

: One pre-dose blood sample will be drawn just before the IMP daily intake at Week 12, Week 24 and Week 36 (visits V4, V6 and V8-EoT) and one sample between 1h and 4h post-dose at Week 36 (last IMP intake, V8- EoT).

Figure 2. Screening period examination flow

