#### 8.2.3 Other Efficacy Parameters

The following parameters will be also determined at various timepoints to further assess efficacy:

- Liver enzymes: ALT, AST, gamma-glutamyl transferase (GGT), alkaline phosphatase (ALP)
- Measured metabolic parameters: fasting plasma glucose (FPG), HbA1c, serum insulin, C-peptide, adiponectin, total cholesterol, low-density lipoprotein cholesterol (LDL-c), high-density lipoprotein cholesterol (HDL-c), triglycerides and free fatty acids (FFA)
- Insulin resistance indexes: Homeostasis model assessment of insulin resistance (HOMA-IR), Quantitative insulin sensitivity check index (QUICKI), Homeostasis model assessment of  $\beta$ -cell function (HOMA- $\beta$ ) and Adipose tissue insulin resistance (Adipo-IR)

HOMA-IR, QUICKI, and HOMA- $\beta$  will be calculated using the fasting C-peptide and FPG values at visits specified in *Table 1*. Adipo-IR will be calculated using the fasting insulin and FFA values at visits specified in *Table 1*.

The HOMA-IR is calculated as [25]:

$$\text{Serum C-peptide (ng/mL)} \times \text{FPG (mg/dL)} / 405$$

The QUICKI is calculated as [26]:

$$1 / (\log(\text{FPG (mg/dL)}) + \log(\text{C-peptide (ng/mL)}))$$

The HOMA- $\beta$  is calculated as [25]:

$$(\text{Serum C-peptide (ng/mL)} \times 360) / (\text{FPG (mg/dL)} - 63)$$

The Adipo-IR is calculated as [27]:

$$\text{Fasting serum FFA (mmol/L)} \times \text{Fasting serum insulin (\muIU/mL)}$$

- Biomarker of inflammation: hsCRP (assessed as part of Section 8.3.6.1 Standard Safety Laboratory Panel (Blood and Urine))
- Biomarkers of fibrosis: N-terminal type III collagen propeptide (pro-C3), NAFLD Fibrosis score (NFS), Fibrosis 4 (FIB-4) score and Enhanced Liver Fibrosis (ELF) score

The NFS is based on a combination of clinical and laboratory measurements (i.e. age, glycemia, BMI, platelet, albumin and AST/ALT ratio). This score has been validated in a large cohort of patients with biopsy-proven NAFLD ( $> 700$  patients) [28].

NFS is calculated as [28]:

$$1.675 + 0.037 \times \text{age (years)} + 0.094 \times \text{BMI (kg/m}^2\text{)} + 1.13 \times \text{Impaired Fasting Glucose or Diabetes (yes =1; no=0)} + 0.99 \times \text{AST/ALT ratio} - 0.013 \times \text{platelet (10}^9\text{/L)} - 0.66 \times \text{albumin (g/dL)}$$

The FIB-4 score is based on a combination of clinical and laboratory (i.e. age, platelets, AST, ALT). This score has been created and validated in different cohorts of patients [29, 30].

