6.1 Time Points and Visit Windows

Day 1 is defined as the day of randomization. Relative days after Day 1 are calculated as (assessment date – Day 1 date) + 1. Relative days prior to Day 1 are calculated as (assessment date – Day 1 date). The day prior to Day 1 is Day -1.

To maximize the data available for analysis, where possible, results from ET and Unscheduled Visits will be allocated to scheduled visit according to the following rules and visit windows described in Table 2.

- If a valid value exists for the scheduled visit to which the ET/Unscheduled Visit has been allocated then the value from the scheduled visit will be used in the analysis, otherwise the values from the ET/Unscheduled Visits will be used in the analysis for the particular scheduled visit.
- If more than one ET/Unscheduled Visit is allocated to the same scheduled visit (and no valid value from the scheduled visit is available) then the closest visit value will be used in the analysis for the scheduled visit.

Visit Windowing rules are defined according to parameters groups in **Table 1** - **Visit window groups** and the windows in **Table 2**.

Double-blind treatment period is defined as the period between the randomization visit (V1) and the EoT visit (V8). Follow-up period is defined as the period between the EoT visit (V8) and the EoS visit (V9).

Table 1 - Visit window groups

Visit window group	Visits	Parameters
Group 1	All visits	Pitting edema assessment, vital signs and body measurements, physical examination
Group 2	Screening, V1, V4, V6, V8	HbA1c
Group 3	Screening, V1, V4, V6, V8, V9	Safety lab, FPG
Group 4	Screening, V1, V5, V8, V9	ECG
Group 5	Screening, V8	DXA, MRI-PDFF, Liver biopsy
Group 6	Screening, V1, V8	eGFR
Group 7	Screening, V1, V5, V9	Pregnancy test
Group 8	V1, V4, V6, V8	Measured metabolic parameters, insulin resistance indexes
Group 9	V1, V8	Fibrosis biomarkers, biobanking sampling

Statistical Analysis Plan

Sponsor Name: Poxel
Sponsor Protocol ID: PXL065-003

Table 2 - Visit windows

Visits	Study day ^a	Group 1	Group 2	Group 3	Group 4	Group 5	Group 6	Group 7	Group 8	Group 9
Screening	N/A	-∞ to -1	-∞ to -1	-∞ to -1	-∞ to -1	-∞ to -1	-∞ to -1	-∞ to -1		
Randomization	1	1 to 12	1 to 43	1 to 43	1 to 64		1 to 127	1 to 64	1 to 43	1 to 127
Week 3	22	13 to 33								
Week 6	43	34 to 64								
Week 12	85	65 to 106	44 to 127	44 to 127					44 to 127	
Week 18	127	107 to 148			65 to 190			65 to 197		
Week 24	169	149 to 190	128 to 211	128 to 211					128 to 211	

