$$141 \times \min(Scr/\kappa, 1) \alpha \times \max(Scr/\kappa, 1) - 1.209 \times 0.993 \text{Age} \times 1.018 \text{ [if female]} \times 1.159 \text{ [if black]}$$

Scr is serum creatinine (mg/dL), κ is 0.7 for females and 0.9 for males, α is -0.329 for females and -0.411 for males, min indicates the minimum of Scr/ κ or 1, and max indicates the maximum of Scr/ κ or 1.

CKD stages are defined as:

- CKD stage 1 (eGFR ≥ 90 mL/min/1.73m 2)
- CKD stage 2 (eGFR ≥ 60 to < 90 mL/min/1.73m 2)
- CKD stage 3a (eGFR ≥ 45 to < 60 mL/min/1.73m 2)
- CKD stage 3b (eGFR ≥ 30 to < 45 mL/min/1.73m 2)
- CKD stage 4 (eGFR ≥ 15 to < 30 mL/min/1.73m 2)
- CKD stage 5 (eGFR < 15 mL/min/1.73m 2)

Shift tables from baseline will be presented at each post-baseline visit showing the number of patients per treatment group with each populated CKD stage for the Safety set.

eGFR data will be summarized by treatment group and visit using standard descriptive statistics, changes from baseline will also be summarized. Summary tables will be produced for the Safety set.

A listing of eGFR data will be produced for the Safety set with site 065-S .

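### After baseline, eGFR, FIB-4 and NFS are scheduled only at Week 36, although their inputs are also collected at Week 12, Week 24, V9 and early termination; a minor, inexpensive loss of derived data

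*SAP*

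**What the plan says.** **Schedule.** Protocol Table 1 and SAP Appendix A mark eGFR at Screening, V1 and V8, and fibrosis biomarkers at V1 and V8. Neither is marked at V4, V6, V9 or ET, and the ET procedure list in Protocol 7.4 omits both. SAP 6.1, Table 1 repeats this: Group 6 (eGFR) is "Screening, V1, V8", and Group 9 (V1 and V8) is "Fibrosis biomarkers, biobanking sampling". FIB-4 and NFS share their row with the two assayed markers, pro-C3 and ELF; the Protocol Table 1 footnote begins "Fibrosis biomarkers include: N-terminal type III collagen propeptide (pro-C3), Nonalcoholic Fatty Liver Disease (NALFD) Fibrosis Score (NFS), Fibrosis 4 (FIB-4) score".

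**Inputs.** Protocol 8.2.3 builds FIB-4 from four items ("i.e. age, platelets, AST, ALT"). For NFS it says: "The NFS is based on a combination of clinical and laboratory measurements (i.e. age, glycemia, BMI, platelet, albumin and AST/ALT ratio". Protocol 8.3.6.3 computes eGFR from serum creatinine, age, sex and race.

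**Analysis.** SAP 7.6.3 analyses the four fibrosis markers by linear regression on treatment, the two stratification factors and the baseline value: "Biomarkers of fibrosis (pro-C3, NFS, FIB-4 and ELF score) will be analyzed using a linear regression with the following covariates". It states no imputation. For eGFR, SAP 7.7.3.2 says: "Shift tables from baseline will be presented at each post-baseline visit showing the number of patients per treatment group with each populated CKD stage".

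**The concern.** FIB-4, NFS and eGFR are arithmetic on results that the trial already collects. Placing FIB-4 and NFS in the same row as pro-C3 and ELF ties them to the schedule of markers that need their own assay.

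Two things follow. First, the CKD shift table is worded for several post-baseline visits but has one scheduled visit, so a patient who withdraws contributes no scheduled post-baseline CKD stage. Second, the FIB-4 and NFS comparisons rest in effect on patients who reach Week 36, although many of those who do not will have the components in the database.

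The SAP also treats results from one blood draw differently without giving a reason. ALT and AST (SAP 7.6.2.3) and hsCRP (SAP 7.6.3) come from the safety panel and get a mixed model over all time points. FIB-4, computed from that same AST and ALT plus platelets and age, gets a regression with one post-baseline time point.

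**Working it through.** **1. Match inputs to visits** (Protocol Table 1; panel contents in Protocol 8.3.6.1 and SAP 7.7.3.1).

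| Item | Screening | V1 | V4 | V6 | V8 | V9 | ET |
|---|---|---|---|---|---|---|---|
| eGFR, as scheduled | X | X | | | X | | |
| FIB-4 and NFS, as scheduled | | X | | | X | | |
| Safety panel (creatinine, AST, ALT, albumin, thrombocytes) | X | X | X | X | X | X | X |
| FPG | X | X | X | X | X | X | X |
| BMI | X | X | X | X | X | X | X |

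Age, sex, race and diabetes status are on file. All three scores can therefore be computed at V4, V6, V9 and ET with no new sample.

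**2. Check the windows** (SAP 6.1, Table 2). For Groups 6 and 9, Days 1 to 127 are labelled Randomization and Day 128 onward is Week 36. The rule moves ET and unscheduled results into these windows, but no eGFR or fibrosis score is scheduled at ET, so only an unscheduled value could be carried. For Group 3 (safety panel, FPG), Days 1 to 43 are Randomization, 44 to 127 Week 12, 128 to 211 Week 24, 212 to 260 Week 36, and 261 onward Week 38.

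**3. Reproduce the plan's figures.** With a difference of 30, SD 30 and two-sided alpha 0.05, the two-sample t-test has power 0.8997 at 22 per arm and 0.9125 at 23, so the stated 23 is right. The synopsis asks for 96 evaluable patients: 96/0.8 = 120. Planned dropout is 0.20 × 120 = 24, or 6 per arm of 30.

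**4. Patients with a post-baseline score.** Under the plan: 120 − 24 = 96. The documents do not give the share *f* of dropouts with a usable earlier or ET central-laboratory result, so it is varied from 0 to 1. The number becomes 96 + 24*f*:

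| *f* | 0 | 0.25 | 0.5 | 0.75 | 1 |
|---|---|---|---|---|---|
| Patients with a value | 96 | 102 | 108 | 114 | 120 |

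**5. Precision of an arm mean at Week 36.** Let 24 of 30 patients have a Week 36 value, and let all 30 have earlier values that explain a share R² of the Week 36 variance left after baseline adjustment. Then

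variance = σ²[(1 − R²)/24 + R²/30] = (σ²/24)(1 − 0.2R²), and the SE ratio is √(1 − 0.2R²).

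Assume baseline, interim and Week 36 values are equally correlated at *r*. After removing baseline, the correlation between any two later values is p = r/(1 + r). One earlier value gives R² = p²; two give R² = 2p²/(1 + p).

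| *r* | p | Earlier values | R² | SE ratio | Reduction |
|---|---|---|---|---|---|
| 0.5 | 0.333 | 1 | 0.111 | 0.989 | 1.1% |
| 0.5 | 0.333 | 2 | 0.167 | 0.983 | 1.7% |
| 0.8 | 0.444 | 1 | 0.198 | 0.980 | 2.0% |
| 0.8 | 0.444 | 2 | 0.274 | 0.972 | 2.8% |

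The result is about 1% to 3%, assuming every dropout has a usable earlier value. If only half do (27 of 30), 0.2 becomes 1 − 24/27 = 0.111, and the range across these rows is 0.6% to 1.5%.

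**The case against.** The strongest reply is that little of importance is lost. Creatinine, AST, ALT, albumin and thrombocytes are summarised by visit with change from baseline in the Safety Set (SAP 7.7.3.1), and ET results are windowed in. ALT and AST also get the mixed model, and patients meeting the predefined elevation limits are listed. FIB-4 and NFS are exploratory, defined as change at Week 36, and one model for all four fibrosis markers is coherent. The eGFR output is descriptive, and Protocol 9.1 describes the trial as a Phase 2 study for internal decision. All of this stands. It limits the point to the derived scores and makes it minor.

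Recovery is also incomplete. Patients lost to follow-up are not asked for an ET visit (Protocol 5.8.2). SAP 2.4 allows local laboratory tests under the COVID-19 memo, and SAP 7.7.3.1 puts local results in listings without summarising them. An ET sample by Day 43 falls in the Group 3 Randomization window. So 24 is a ceiling.

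A reader might infer three stronger things that the documents do not support:

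- **That dropouts can have no post-baseline value at all.** Protocol 8.3.6 permits unscheduled central-laboratory tests, and the SAP 6.1 windows can carry them. Only a scheduled value is missing, and the Week 36 window opening at Day 128 is not an error.
- **That a renal signal in withdrawing patients is lost.** Their creatinine is reported; what is missing is its conversion to a CKD stage.
- **That the SE would fall by 2.5% to 6.6%.** This puts raw correlations of 0.5 and 0.8 into the formula of step 5 and ignores the baseline adjustment already in the regression.

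**Conclusion.** The point holds, and its severity is minor. From baseline onward the plan schedules eGFR, FIB-4 and NFS only at V1 and Week 36 (eGFR also at Screening), while their inputs are collected at four further post-baseline points: Week 12, Week 24, V9 and ET. No stated reason accounts for this.

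Up to 24 of 120 planned patients are affected. The 24 uses the planned number randomised; the SAP's main sets also exclude undosed patients and one site, so the realised number will differ. The SE gain of about 1% to 3% rests on equal correlations of 0.5 to 0.8 and on a usable earlier value for every dropout. The other gain is less selection towards completers, which the documents do not allow to be quantified.

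That the FIB-4 and NFS regression uses only patients with a Week 36 value is a likely inference rather than a stated rule: SAP 7.6.3 is silent on missing data for it, and the sample code is redacted.

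**What to change.** In the SAP:

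1. Derive eGFR, FIB-4 and NFS by program from central-laboratory components at V4, V6, V8, V9 and ET, and move them to the Group 3 windows in SAP 6.1.
2. Show the CKD shift table at these visits, with ET results allocated by window. Add a worst post-baseline row that uses every sample after the first dose regardless of window, so that ET samples on Days 2 to 43 are not lost to the Randomization window.
3. Analyse FIB-4 and NFS with the SAP 7.6.2.3 mixed model on V4, V6 and V8, reporting Week 36 as the contrast.
4. Leave pro-C3 and ELF as they are, since they need their own assays.
5. Record the change in SAP Section 8.

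The cost is a little programming, and FIB-4 and NFS would then use a different model from pro-C3 and ELF. No sample, visit or patient is added.
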